## **Design**

Given the exploratory nature of this investigation aimed at generating preliminary efficacy and safety data for a specific PRP preparation method, a single-arm design was chosen. This single-arm trial enrolled 201 male AGA patients receiving 3-5 sessions of autologous apheresis PRP injections. The primary endpoint, change in the BASP classification, was assessed by independent, blinded physicians. Patient-reported outcomes were assessed one month after treatment completion using a four-item questionnaire covering hair quality, hair thickness, hair loss reduction, and overall satisfaction. Associations between treatment response and key variables, including age, number of sessions, baseline severity, and PRP cellular composition were analyzed.

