## **Assessment Criteria**

The severity of hair loss was graded using the Basic and Specific (BASP) classification criteria. Briefly, mild cases included patterns M1, M2, C1, V1, or F1; moderate cases included M3, C2, V2, V3, F2, or F3; severe cases were defined as C3

or any U-type pattern. Coexistence of basic and specific types resulted in an upgrade to the next severity level. Based on grading by blinded, independent physicians using standardized photographs, a positive response was defined as an improvement of at least one grade in either the Basic or Specific component of the BASP system from Baseline to the day of the last treatment. When the physician-assessed gradings were inconsistent, disagreements were resolved by a third blinded assessor, with the final outcome determined by a majority decision.

Patient-reported outcomes were assessed via telephone or outpatient visit one month after treatment completion using a four-item questionnaire covering hair quality, hair thickness, hair loss reduction, and overall satisfaction. Responses are recorded on a 3-point scale: -1 (deteriorated/dissatisfied), 0 (unchanged/neutral), +1 (improved/satisfied). The outcome will be reported as the proportion of participants reporting an improvement (score of +1) for each individual item. Adverse reactions during the treatment process were recorded.

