### **Statistical Analysis**

Statistical analysis was performed using SPSS 26.0 and Prism 9.0 software. Continuous variables were tested for normality (Shapiro-Wilk test) and were presented as mean  $\pm$  SD or median (IQR), as appropriate. Categorical variables were expressed as n (%). Binary Logistic Regression Analysis was used to analyze the relationship between the effectiveness of PRP injection treatments and age, treatment sessions, initial severity at diagnosis, and cellular components in PRP. A crosstabulation analysis was conducted to assess the association between treatment

sessions and clinical effectiveness. Chi-square test was used to analyze the impact of treatment sessions on effectiveness, and Mantel-Haenszel Chi-square test was used to assess for a linear trend. Receiver Operating Characteristic (ROC) curve analysis was conducted to assess the predictive utility of PRP RBC concentrations for treatment failure (defined as 'no improvement'). A two-sided p-value of  $< 0.05$  was considered as statistical significance.

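### The session count also fixes when response is read, so the planned session analyses cannot separate more sessions from more elapsed time or from response-related continuation

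*Protocol*

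**What the plan says.** Assessment Criteria: a positive response is a gain of at least one grade in either BASP component, measured "from Baseline to the day of the last treatment".

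Interventions, Blinding, and Randomization: scalp photographs are taken before each injection, and injections are 3 to 5 weeks apart.

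Design: "This single-arm trial enrolled 201 male AGA patients receiving 3-5 sessions of autologous apheresis PRP injections". The Interventions section gives three or more with no upper limit, so the two statements should be reconciled. The only rule on session number is the minimum of three, written as an exclusion criterion under Participants. Nothing says how a patient came to have 3, 4 or 5.

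Statistical Analysis uses the session count in three ways:
- "Binary Logistic Regression Analysis was used to analyze the relationship between the effectiveness of PRP injection treatments and age, treatment sessions", together with initial severity and PRP cell components. Time on treatment is not among the covariates.
- "Chi-square test was used to analyze the impact of treatment sessions on effectiveness".
- "Mantel-Haenszel Chi-square test was used to assess for a linear trend".

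Elsewhere the wording is more cautious. Design opens "Given the exploratory nature of this investigation aimed at generating preliminary efficacy and safety data" and lists "Associations between treatment response and key variables, including age, number of sessions". Statistical Analysis itself also has "A crosstabulation analysis was conducted to assess the association between treatment" sessions and effectiveness.

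**The concern.** Because the outcome is read on the last treatment day, a patient with five sessions has had roughly twice as long to change as one with three. A higher response rate at five sessions could therefore reflect the extra sessions or a delayed effect of the earlier ones. It could also reflect selection, if patients who were already improving tended to carry on. The opposite pattern is equally possible, if patients who had improved tended to stop. The document says nothing on whether continuation depended on response, or in which direction.

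The Objective makes identifying key predictors an aim of the study, and Design names session number among the variables. Followed as written, the plan can produce a significant session trend when additional sessions do nothing, and Statistical Analysis would report it as an impact. Readers could take it as evidence that more sessions work better.

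**Working it through.** **Timing of the reading.** With k sessions and 3 to 5 weeks between them, the last treatment day falls (k−1)×3 to (k−1)×5 weeks after the first. Because photographs precede each injection, k−1 injections have been given by then.

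| Sessions k | Weeks to reading | Mid-range | Injections before reading |
|---|---|---|---|
| 3 | 6–10 | 8 | 2 |
| 4 | 9–15 | 12 | 3 |
| 5 | 12–20 | 16 | 4 |

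The windows overlap at weeks 9–10 and 12–15. Simulated with equal groups, sessions and weeks correlate at about 0.96 if each interval varies independently between 3 and 5 weeks, a variance inflation factor 1/(1−r²) of about 12. If each patient keeps one interval, the correlation is about 0.88 and the factor about 4.

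**Size of the distortion.** The document states no response rate, group sizes, time course or continuation probabilities, so what follows is illustration. Common inputs: N = 201 (Design), two-sided 0.05 (Statistical Analysis), no effect of additional sessions. The trend statistic is (N−1)r², referred to chi-square on 1 df.

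*(a) Response depends on elapsed time alone.* Assume F(t) = c(1 − exp(−λt)) with ceiling c, λ set so that F(8) = 40%, and equal groups of 67. Then F(t) = c[1 − (1 − 0.40/c)^(t/8)]. At weeks 8, 12 and 16:
- c = 100%: 1 − 0.6 = 40%; 1 − 0.6^1.5 = 54%; 1 − 0.6² = 64%.
- c = 60%: 40%; 0.60(1 − 0.333^1.5) = 48%; 0.60(1 − 0.333²) = 53%.
- c = 50%: 40%; 0.50(1 − 0.2^1.5) = 46%; 0.50(1 − 0.2²) = 48%.
- c = 45%: 40%; 0.45(1 − 0.111^1.5) = 43%; 0.45(1 − 0.111²) = 44%.

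Simulation with intervals uniform on 3–5 weeks gives these rejection rates:

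| Ceiling | Trend test | Logistic model, test for sessions |
|---|---|---|
| none (100%) | 79% | 79% |
| 60% | 32% | 35% |
| 50% | 15% | 13% |
| 45% | 8% | 8% |

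The trend column is from 4,000 runs per setting; repeat runs agree within about three percentage points, and a constant interval per patient gives 78, 31, 14 and 8%. The logistic column is from 1,000 runs of a model with sessions, age and severity. Age and severity are assumed unrelated to response and session count, and PRP components are left out.

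Over 10–50% response by week 8 and four group splits (67/67/67, 100/61/40, 40/61/100, 140/41/20), the trend test rejects in 26–85% with no ceiling. It rejects in 17–40%, 12–17% and 7–10% if response plateaus 20, 10 or 5 points above its week-8 value. The Pearson chi-square gives 17–77%, 12–32%, 8–14% and 6–10% in the same order.

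*(b) Response fixed by session 3, continuation depends on it.* At each of two steps the patient continues with a probability that differs between responders and non-responders. To show the mechanism, take 60% responders with 0.7 versus 0.5:
- stop at 3: 0.6×0.3 = 0.18 responders, 0.4×0.5 = 0.20 non-responders, apparent response 0.18/0.38 = 47%;
- stop at 4: 0.6×0.7×0.3 = 0.126 and 0.4×0.5×0.5 = 0.10, giving 56%;
- reach 5: 0.6×0.7² = 0.294 and 0.4×0.5² = 0.10, giving 75%.

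The later sessions contributed nothing to this gradient. With 30% and 50% responders (10,000 runs) the trend test rejects as follows:

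| Continuation, responders vs non-responders | Rejection |
|---|---|
| 0.60 vs 0.60 | 5% |
| 0.62 vs 0.58 | 10–11% |
| 0.65 vs 0.55 | 37–44% |
| 0.70 vs 0.50 | 91–95% |

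Swapping the two probabilities gives the same ranges with a falling trend. At equal continuation the test holds its nominal level, so the fault lies in what is fed to it, not in the test.

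**The case against.** The best reply has five parts.

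1. **The study is exploratory and mostly speaks of association.** True. Only the one word *impact* claims more. But looking for predictors is a stated aim, and relabelling alone would not tell the reader what the association is made of. Nor is the final session count a baseline predictor unless it was fixed in advance, which the document does not say.
2. **A predictor need not be separated from elapsed time, since longer courses take longer.** This has force against the time argument. It does not answer response-related continuation, where the outcome would help determine the predictor.
3. **The windows overlap, so weeks could be added to the model.** Possible, but not planned and weakly identified. It would not remove selection.
4. **The size rests on assumed inputs.** This stands in full. The largest time-only figures need response to keep climbing with no ceiling. The Objective calls the condition progressive, so improvement with time would have to be a delayed effect of earlier injections. With an early plateau the distortion is small. The simulations show that the distortion can be anywhere from negligible to large, not which applies here.
5. **That the reading follows k−1 injections is inferred.** It follows from photographs being taken before each injection. Assessment Criteria does not say which last-day image is graded, so the sponsor should confirm it.

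**Conclusion.** The point holds and should be fixed. The document itself ties the reading time to the session count, sets only a minimum for that count, and plans three session analyses without a time term. As planned, they cannot separate sessions from time on treatment or from response-related continuation. This conclusion rests on the text and does not depend on any simulated figure.

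Under assumed inputs and no effect of extra sessions, false rejection at the 5% level runs from about 7% to 85% for the time-only mechanism and from about 10% to 95% for unequal continuation. Whether continuation depended on response, and in which direction, is unknown.

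The damage is confined to the session results, including the session term in the regression. The overall proportion responding on the last treatment day remains valid as a description, though it pools readings from about 6 to 20 weeks.

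**What to change.** 1. Keep the defined response and its regression. Confirm and state that the reading reflects k−1 injections, and tabulate weeks from first injection to reading by session count.
2. Add, labelled as a post hoc sensitivity analysis, the BASP response at the photograph taken before the session-3 injection. Every analysed patient should have it, since three sessions are the minimum and photographs precede each injection. Fit the predictor model to it without session count, and tabulate it by eventual session count. A difference there cannot come from later sessions and points to selection, though it may also reflect baseline severity or interval lengths that differ between groups. With time-only response and assumed interval lengths differing by session count, that table rejects in about 7–14% of trials, against 4–6% without such a difference. No difference does not exclude selection: in setting (b) the table misses 0.65 versus 0.55 in about 56–63% of trials and 0.62 versus 0.58 in about 90%.
3. State how the session count came about, and replace *impact* in Statistical Analysis with *association*. Present the session tests as descriptive and confounded with time on treatment, with no conclusion that more sessions work better.

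The cost is small: no new visits or data collection, blinded grading of any session-3 photographs not yet graded, one table, one model and a change of wording. The session-3 reading has limits: it spans about 6–10 weeks, reflects only two injections, is post hoc and detects only strong selection. It supplements the defined response and does not replace it.

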### **Statistical Analysis**

Statistical analysis was performed using SPSS 26.0 and Prism 9.0 software. Continuous variables were tested for normality (Shapiro-Wilk test) and were presented as mean  $\pm$  SD or median (IQR), as appropriate. Categorical variables were expressed as n (%). Binary Logistic Regression Analysis was used to analyze the relationship between the effectiveness of PRP injection treatments and age, treatment sessions, initial severity at diagnosis, and cellular components in PRP. A crosstabulation analysis was conducted to assess the association between treatment

sessions and clinical effectiveness. Chi-square test was used to analyze the impact of treatment sessions on effectiveness, and Mantel-Haenszel Chi-square test was used to assess for a linear trend. Receiver Operating Characteristic (ROC) curve analysis was conducted to assess the predictive utility of PRP RBC concentrations for treatment failure (defined as 'no improvement'). A two-sided p-value of  $< 0.05$  was considered as statistical significance.

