## **Objective**

Androgenetic alopecia (AGA) is a progressive condition with limited optimal therapeutic options. While platelet-rich plasma (PRP) therapy has been explored, the apheresis technique offers a distinct method of PRP preparation that yields higher platelet purity and more consistent cellular composition compared to conventional centrifugation methods. This study is specifically designed to evaluate the clinical effectiveness of this autologous apheresis PRP and identify key predictors.

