## **Methods**

### **Participants**

Eligible participants were required to meet all of the following criteria: (1) Male aged 18-55, who had history of hair loss more than 6 months and was diagnosed with AGA based on Chinese guideline for diagnosis and treatment of AGA. (2) General health: in good health with a body weight  $\geq 50$  kg, no history of hypertension, diabetes, platelet dysfunction, or any other contraindication to PRP apheresis. (3) Treatment naivety: no use of finasteride, minoxidil, or any other treatment for hair loss within

the 6 months preceding enrollment. Additionally, participants must have had no recent use of glucocorticoids (topical to treatment site for 1 month; systemic for 2 weeks) or nonsteroidal anti-inflammatory drugs (within 48 hours) prior to PRP apheresis. (4)

Laboratory parameters: blood tests within 2 weeks before PRP apheresis meeting the following criteria: hemoglobin concentration > 120 g/L, hematocrit 0.30-0.50, platelet counts > 110 × 10^9/L. No clinically significant abnormalities in inflammation, coagulation, or electrolyte panels.

Exclusion criteria: (1) Concurrent Hair Loss Treatments: Concurrent use of finasteride, minoxidil, and other hair growth treatments during PRP treatments. (2) Incomplete treatment protocol: failure to complete a minimum of 3 consecutive PRP treatment sessions as per the study protocol, or failure to complete follow-up for any reason.

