## **Treatment Protocol**

Autologous PRP was prepared using a closed-system blood cell separator (NGL XCF 3000, Nigale Biomedical, China) with disposable blood cell collection consumables, following the manufacturer's standardized protocol. Approximately 20–50 mL of PRP was harvested per session, of which 2 mL was used for quality control and the remainder was aseptically aliquoted into five sterile bags and stored at –80°C. Cellular components were quantified using an automated hematology analyzer (760CS, Mindray, China). Prior to injection, the treatment area was cleansed with sterile gauze. Topical anesthesia was achieved by applying compound lidocaine cream. Subsequently, the scalp was disinfected with 75% medical-grade alcohol. Frozen PRP aliquots were thawed to room temperature immediately before use. Using a 30-gauge sterile needle, rewarmed autologous PRP was administered via intradermal and subcutaneous injections at multiple points across the treatment area, with an injection volume of 0.05 mL per point at intervals of approximately 0.5 cm. Following the procedure, the scalp was cleansed and disinfected again. Participants were advised not to wash hair for the first 48 hours after treatment. In the event of minor bleeding or fibrin deposition at injection sites, gentle cleansing with sterile gauze was recommended.

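### A cheap improvement, not an error: the predictor analysis of autologous PRP composition does not use the man's own screening blood counts, so an association cannot be attributed to the product

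*Protocol*

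**What the plan says.** The Objective is to "evaluate the clinical effectiveness of this autologous apheresis PRP and identify key predictors". The Treatment Protocol section states that "Autologous PRP was prepared using a closed-system blood cell separator", so each treated man is his own donor, and that "Cellular components were quantified using an automated hematology analyzer".

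Under Statistical Analysis, binary logistic regression relates effectiveness to "age, treatment sessions, initial severity at diagnosis, and cellular components in PRP". A ROC analysis is then planned to "assess the predictive utility of PRP RBC concentrations for treatment failure". The Design section names the same four groups of variables.

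The man's own blood appears only under Participants, as an eligibility condition: "blood tests within 2 weeks before PRP apheresis meeting the following criteria", namely "hemoglobin concentration > 120 g/L, hematocrit 0.30-0.50, platelet counts > 110" × 10^9/L. The protocol names these values neither as covariates nor as comparators for the ROC curve, and it nowhere expresses PRP content relative to the donor's count.

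**The concern.** In an autologous product, a cell concentration can carry two kinds of information: how well the separation worked, and what the man's blood was like to begin with. Eligibility leaves room for the second, since hematocrit may lie anywhere from 0.30 to 0.50 and the platelet limit has no upper end.

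Suppose high PRP RBC goes with non-response. The listed analysis cannot say whether the red cells in the product matter or whether men with a higher hematocrit respond less. The first would bear on how PRP is prepared. The second would be known from a routine blood test before any apheresis. Because the study is about one preparation method, readers will be drawn to the first. There is also a purely predictive loss: candidate predictors that are available earlier, from tests already required, are left out.

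**Working it through.** The protocol gives no figure on this point to reproduce, so the check is a simulation of what omitting the donor count could do.

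**From the protocol:** n = 201 (Design); logistic regression and two-sided 0.05 (Statistical Analysis).

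**Assumed, not in the documents:** response about 60%; correlation r between donor count and PRP component; donor odds ratio (OR) per SD for response.

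**Model:** donor count D ~ N(0,1); PRP component X = r·D + √(1 − r²)·noise; logit P(response) = a + ln(OR)·D. X has no effect of its own. There were 2,000 trials per setting, each fitted with X alone and with X plus D.

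Apparent OR per SD of X, and share of trials with p < 0.05, when D is left out:

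| Donor OR per SD | r = 0.3 | r = 0.5 | r = 0.7 |
|---|---|---|---|
| 1.3 | 1.08; 7.7% | 1.14; 14.1% | 1.20; 23.2% |
| 1.5 | 1.13; 13.6% | 1.23; 27.6% | 1.33; 46.4% |
| 2.0 | 1.21; 24.5% | 1.39; 58.8% | 1.60; 86.2% |

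With D in the model, the share is 4.6% to 5.7% throughout.

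**Second simulation** (response 50% or 70%; r = 0.2, 0.5, 0.8; an age covariate in both models):
- Donor OR 1.0: 4% to 6% without D, so no bias.
- r = 0.2, donor OR 1.3 to 1.5: 6% to 8%.
- r = 0.5, donor OR 1.3 to 1.5: 13% to 27%.
- With D added: 4.2% to 5.6% in every setting.

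**Cost in precision.** To a first approximation the standard error of the PRP coefficient grows by 1/√(1 − r²):
- r = 0.3: 1/√0.91 = 1.05
- r = 0.5: 1/√0.75 = 1.15
- r = 0.7: 1/√0.51 = 1.40

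The simulated increases are 6–9%, 16–18% and about 40%. The small excess over the formula at r = 0.3 and 0.5 is expected in a logistic model at this sample size.

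**Imperfect proxy.** No RBC count is listed among the screening criteria, so hematocrit or hemoglobin must stand in for it, taken up to 2 weeks earlier. If the proxy has an assumed reliability of 0.6, the adjusted model still finds X significant in about 8% of trials (r = 0.5, OR 1.5) and 31–32% (r = 0.7, OR 2.0). At reliability 0.8 the shares are about 6% and 13%.

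**If the product effect is real** (product OR 1.5 per SD, no donor effect), power for X falls from about 78% unadjusted to 65–67% at r = 0.5 and about 50% at r = 0.7 after adjustment.

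**The case against.** The strongest reply is that the protocol does not claim causation. It speaks of predictors, associations and predictive utility, and calls the work exploratory. A marker that partly carries a donor trait is still a marker, and the PRP RBC ROC curve is correct whatever lies behind it. In the simulation, the association between X and response is real in the marginal sense. It is false only if read as an effect of X. This stands, and it is why the point is an improvement and not an error.

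The two links are also unsupported. Nothing in the protocol shows that donor counts affect hair response or that product counts follow donor counts after separation. The Objective's statement that apheresis gives a more consistent composition leans against strong tracking, and separation quality may drive residual RBC more than the donor does. The eligibility limits show the permitted range, not the actual spread. This stands too, so the size of any bias is unknown and may be zero.

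On scope, further models may sit in an analysis plan that is not shown, and the Design section's list of variables is not worded as closed. That is fair, but the protocol does state the predictors of the logistic model and the single variable of the ROC analysis, and the comment is on those.

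A reader might go further and infer that the planned model is wrong, that a PRP RBC association would be spurious, or that a product effect should count only if it stays significant after adjustment. The documents support none of these. The first two need both unproven links. The third would discard real effects, given the power loss shown above, while the imperfect proxy means that surviving adjustment does not prove a product effect either.

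**Conclusion.** The omission is real and the remedy is cheap, but the planned analysis contains no mistake. As pure prediction it stands. What it cannot do is separate an effect of PRP composition from a trait of the man whose blood was used.

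The size depends on two assumed quantities. Over r = 0.3 to 0.7 and donor OR 1.3 to 2.0 per SD, a component with no effect of its own reaches significance in about 8% to 86% of trials, and in about 28% at the middle setting (r = 0.5, OR 1.5). The top of that range needs both quantities at their highest. If the donor OR is 1.0, the rate stays at about 5%.

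**What to change.** In Statistical Analysis:

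1. Keep the planned logistic model. Add a second one that also contains screening hematocrit (or hemoglobin) and screening platelet count.
2. Report each PRP component's odds ratio with its interval from both models, side by side.
3. Show the ROC curve for screening hematocrit beside the one for PRP RBC.
4. Report a PRP association as predictive only. Discuss any product-quality reading in the light of both models, without a pass/fail rule based on significance after adjustment.

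**Cost:** analysis wording and two covariates, with no new visits or samples. Eligibility required the values; that they were kept as analysis variables is likely but not stated, and should be confirmed. The standard error of the PRP coefficient rises by about 6–9%, 16–18% or 40% at an assumed r of 0.3, 0.5 or 0.7. Residual confounding remains because hematocrit is a proxy measured up to 2 weeks earlier, and the report should say so.

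### Any claim about the number of sessions should rest on a test adjusted for baseline severity and age, not on two crude chi-square tests

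*Protocol*

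**What the plan says.** Under Statistical Analysis, the protocol relates session number to response in three ways:

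- Binary logistic regression, with predictors listed as "age, treatment sessions, initial severity at diagnosis, and cellular components in PRP". One joint model is the natural reading, but the text does not say so outright.
- A Pearson test on the sessions table, in the sentence that opens "Chi-square test was used to analyze the impact of treatment sessions on effectiveness, and Mantel-Haenszel Chi-square test".
- A trend test: "Mantel-Haenszel Chi-square test was used to assess for a linear trend". No stratification factor is named.

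One threshold covers all of them: two-sided p < 0.05 "was considered as statistical significance". The section does not say which result decides if they disagree.

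The Design section states: "This single-arm trial enrolled 201 male AGA patients receiving 3-5 sessions of autologous apheresis PRP injections". It calls the study exploratory, names change in BASP classification as the primary endpoint, and lists session number among the variables examined for association with response. Neither Design nor the section on interventions, blinding and randomization gives a rule for who received three, four or five sessions.

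**The concern.** In a single-arm study without an allocation rule, patients who had five sessions may differ at baseline from those who had three. The protocol itself treats age and initial severity as possible predictors of response, yet the two tests devoted to sessions leave both out. If severity or age is linked to session number and to response, a crude test mixes their contribution with that of sessions.

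The crude and adjusted analyses address different quantities and can disagree. The section words the crude chi-square as a test of impact, so a crude p-value could end up carrying the session claim. Identifying predictors is a stated objective of the study, so readers may act on that claim.

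**Working it through.** **Inputs from the protocol.** N = 201; sessions 3, 4 or 5; binary response; two-sided 0.05 per test. The protocol gives no power or family-wise error figure, so there is nothing to reproduce.

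**Inputs assumed, because the protocol does not give them.** Response rate, session distribution, and the links of severity and age with sessions and with response. The values are stated below. No run contains a true session effect.

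**Tests.**
- Pearson: Q = Σ (y_k − n_k p̄)² / (n_k p̄(1 − p̄)), 2 df.
- Trend: (N − 1)r² = 200r², 1 df.
- Logistic: Wald test of the session term in a model with severity, age and three cell components.

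**Step 1: bounds for three tests.** If independent, 1 − 0.95³ = 14.3%; the sum is 3 × 0.05 = 15%. The tests use the same patients and overlap heavily, so the true figure is lower.

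**Step 2: repetition alone (sessions unrelated to severity and age).** 4,000 trials per setting, with session shares 34/33/33% or 60/25/15%, response 50% or 70%, and sessions coded linearly or as categories in the model:
- Either crude test significant: 6.4-8.0%.
- Any of the three significant: 7.5-9.4%.

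The Monte Carlo standard error at 5% is √(0.05 × 0.95/4000) = 0.34 percentage points. A separate set of 20,000 trials per setting put either crude test at 7.3-7.7%.

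**Step 3: severity and age linked to both sessions and response.** In this set, more severe patients get more sessions and respond less often. Shares are 60/25/15%, baseline response 60%, sessions linear in the model. Log-odds are per severity level / per SD of age.

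| Sessions | Response | Pearson | Trend | Adjusted term | Any of three |
|---|---|---|---|---|---|
| 0.2 / 0.1 | −0.5 / −0.2 | 5.6% | 6.0% | 4.9% | 9.8% |
| 0.2 / 0.1 | −0.8 / −0.3 | 6.1% | 6.9% | 5.6% | 11.5% |
| 0.5 / 0.2 | −0.5 / −0.2 | 8.1% | 9.8% | 5.6% | 14.4% |
| 0.5 / 0.2 | −0.8 / −0.3 | 13.7% | 16.8% | 5.3% | 21.8% |
| 0.8 / 0.3 | −0.5 / −0.2 | 13.0% | 15.7% | 5.9% | 21.3% |
| 0.8 / 0.3 | −0.8 / −0.3 | 24.0% | 30.2% | 4.6% | 35.4% |

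A second set (2,500 trials per setting; severity shares 30/50/20%) lets severity raise both sessions and response. Odds ratios are per level.

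| Sessions OR | Response OR | Crude trend | Any of three |
|---|---|---|---|
| 1.5 | 1.5 | 6.9% | 11.1% |
| 2 | 1.5 | 9.1% | 13.0% |
| 2 | 2 | 17.6% | 22.8% |
| 3 | 1.5 | 15.3% | 21.1% |
| 3 | 2 | 31.9% | 37.6% |

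Here the adjusted term rejected in 4.4-5.6% and a severity-stratified Mantel-Haenszel test in 4.3-5.5%. A further run under severity confounding gave 9-29% for any of the three, with the adjusted and stratified tests at 4-5%.

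**Step 4: direction.** In the first table the crude association tends to make extra sessions look harmful; in the second it tends to make them look helpful. The percentages are two-sided, so they do not measure the chance of falsely claiming that more sessions help.

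**Step 5: follow-up.** Response is read on the day of the last treatment (Assessment Criteria), and sessions are 3 to 5 weeks apart. If baseline is the first session, three sessions span two intervals, 2 × 3 to 2 × 5 = 6-10 weeks. Five sessions span four intervals, 4 × 3 to 4 × 5 = 12-20 weeks. Adjustment for severity and age does not remove this difference.

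**The case against.** The study is declared exploratory, and sessions are one of several secondary associations. Crude results beside an adjusted model are ordinary reporting. A ranking of tests or a multiplicity rule may sit in a statistical analysis plan that is not shown, so its absence from the protocol is no fault. The two chi-square tests also have different stated purposes, overall difference and linear trend, and nothing in the protocol permits a claim whenever any one of them is significant.

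Confounding is bias, not alpha inflation. Where severity drives both variables, a crude association between sessions and response really exists, and a crude test that rejects is right about its own null. The error lies in a causal reading, and no alpha correction addresses it.

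The adjusted test stays near 5% in the simulations because the model contains every confounder that was simulated. The protocol is also written in the past tense; choosing a deciding test once results are known would not restore 5% control.

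All of this stands as a limit on the size of the point. None of it makes an unadjusted test a sound basis for a statement about the impact of sessions when the same section names age and initial severity as candidate predictors. That choice of test is stated in the protocol; it is not a detail left open.

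**Conclusion.** The point holds as one of confounding, with a modest multiplicity component. Session number was not randomised, and two of the three session analyses take no account of baseline severity or age. Repetition alone brings the chance of at least one false-positive session result to about 8-9%.

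A reader might infer that testing sessions three times at 0.05 puts the false-positive rate near 14%, or well above 5% as a matter of fact. The document does not support that. The 14% needs independent tests, and these are strongly correlated. The range of about 9-38% needs severity to have influenced both session number and response, and the protocol gives no data on the size or direction of either link. Nor may a reader assume that the crude tests favour more sessions; they could equally hide a benefit.

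The adjusted term at about 4.4-5.9% rests on severity and age being the only confounders.

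**What to change.** In Statistical Analysis, state that any session claim rests on the session term of one multivariable logistic model that includes baseline severity and age. A Mantel-Haenszel trend test stratified by baseline severity (mild, moderate, severe, as already defined under Assessment Criteria) is an acceptable alternative; name one of the two. Present the crosstabulation and the crude tests as descriptive.

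Replace the impact wording with association, and note that patients with more sessions were also followed for longer before response was read. If the data have already been analysed, say that the deciding test was named afterwards.

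The cost is wording only, with no new data. The downside is that a session result significant only in a crude test can no longer be claimed.
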